APPENDIX II: PROTOCOL CENTRAL MONITORING PLAN

Central monitoring will be required for all patients enrolled at each site. All documents must be uploaded with 2 weeks of the corresponding time point or cycle.

Monitored Data	Protocol Section	CRF Question/ Data Element	Monitoring Conditionality	Source document	CTSU Document Type	Time point
Eligibility						
Confirmation of eligible diagnosis	4.1.5	Does patient have histologic verification of the malignancy at the indicated time point?	Required	E.g., clinical note, laboratory test report, pathology report, etc.	Clinical Note, Laboratory Report or Pathology report	Enrollment
Performance Level	4.1.9	ECOG performance status	Required	E.g., clinical note, eligibility checklist	Clinical Note, Eligibility Determination Checklist	
Adequate Bone Marrow function	4.1.11.1	Does patient have adequate bone marrow function?	Required	Laboratory test report	Laboratory Report	
Adequate Renal Function	4.1.11.2	Does patient have adequate renal function?	Required	Laboratory test report	Laboratory Report	
Adequate Neurologic Function	4.1.11.4	Does patient have adequate neurologic function?	Required	E.g. clinical note	Clinical Note	
Date of Informed Consent	3.5	Date of Informed Consent	Required	Informed consent (redacted signature pages with dates)	Informed Consent	
Drug Administration Elements						
Total BAY 1895344 (elimusertib) dose	5.1	Total Dose:	Required	Medication administration record	Treatment Administration Document	Cycle 1 Cycle 3
Disease Evaluation Elements						
Tumor Disease Evaluation	8.1	Was the patient's disease status evaluated during this reporting period?	Required	E.g. CT report, MRI report, FDG-PET report, PET-CT report	Scan Reports	Cycle 1 Cycle 3
Adverse Event Capture						

THIS PROTOCOL IS FOR RESEARCH PURPOSES ONLY, SEE PAGE 1 FOR USAGE POLICY

Labs/reports documenting protocol specific CTEP-AERS reportable events	13.0	Has an Adverse Event Expedited Report been submitted?	Conditional: If response is YES, CM is required	E.g., hospital admission report, laboratory reports, etc.	Relevant Document	Cycle 1 Cycle 3
--	-------------	--	--	---	-------------------	--------------------

Addressing Monitoring Findings

In the event that this monitoring identifies unacceptable procedures or significant deviations from protocol procedures, then the site will need to submit a corrective action plan to [contact] within two weeks.

In the event of significant repeated major deviations from the protocol, COGQA, in consultation with the study chair, may recommend that COG leadership suspend accrual at the site.

APPENDIX III: CYP3A4 SUBSTRATES, INDUCERS AND INHIBITORS

This is NOT an all-inclusive list. Because the lists of these agents are constantly changing, it is important to regularly consult frequently updated medical references.

CYP3A4 substrates	Strong Inhibitors ¹	Moderate Inhibitors	Strong Inducers	Moderate Inducers
abemaciclib	atazanavir	aprepitant	apalutamide	bosentan
acalabrutinib ⁵	boceprevir	conivaptan	barbiturates	cenobamate
alfentanil ^{4,5}	clarithromycin	crizotinib	carbamazepine	dabrafenib
alprazolam ⁵	ceritinib	diltiazem	enzalutamide	efavirenz
amiodarone ⁴	cobicistat	dronedarone	fosphénytoïn	eslicarbazepine
amlodipine	danoprevir/ritonavir	duvelisib	lumacaftor/	etravirine
aprepitant/fosaprepitant	darunavir	erythromycin	ivacaftor	lorlatinib
atorvastatin	delavirdine	fedratinib	mitotane	modafinil
avanafil ⁵	elvitegravir/ritonavir	fluconazole	phenobarbital	nafcillin
axitinib	grapefruit ³	fosamprenavir	phenytoïn	rifabutin
bortezomib	grapefruit juice ³	fosnetupitant	primidone	rifapentin
bosutinib ⁵	idelalisib	grapefruit ³	rifampin	
brexpiprazole	indinavir/ritonavir	imatinib	St. John's wort	
brigatinib	itraconazole	isavuconazole		
budesonide ⁵	ketoconazole	lefamulin		
buspirone ⁵	lopinavir/ritonavir	letermovir		
cabozantinib	nefazodone	mifepristone		
calcium channel blockers	nelfinavir	netupitant		
cisapride	paritaprevir/ritonavir/	nilotinib		
citalopram/escitalopram	ombitasvir +/- dasabuvir	ribociclib		
cobimetinib ⁵	posaconazole	verapamil		
colchicine ⁵	ritonavir			
conivaptan ⁵	saquinavir			
copanlisib	telaprevir			
crizotinib	telithromycin			
cyclosporine ⁴	tipranavir/ritonavir			
dabrafenib	tucatinib			
dapsone	voriconazole			
darifenacin ⁵				
darunavir ⁵				
dasatinib ⁵				
dexamethasone ²				
diazepam				
dihydroergotamine				
docetaxel				
doxorubicin				
dronedarone ⁵				
ebastine ⁵				
eletriptan ⁵				
eliglustat ⁵				
eplerenone ⁵				
ergotamine ⁴				
erlotinib				
estrogens				
etoposide				
everolimus ⁵				
felodipine ⁵				
fentanyl ⁴				
gefitinib				

CYP3A4 substrates	Strong Inhibitors ¹	Moderate Inhibitors	Strong Inducers	Moderate Inducers
haloperidol ibrutinib ⁵ idelalisib imatinib indinavir ⁵ irinotecan isavuconazole ⁵ itraconazole ivacaftor ketoconazole lansoprazole lapatinib lomitapide ⁵ lorlatinib losartan lovastatin ⁵ lurasidone ⁵ macrolide antibiotics maraviroc ⁵ medroxyprogesterone methadone midazolam ⁵ midostaurin ⁵ modafinil naloxegol ⁵ nefazodone nilotinib nisoldipine ⁵ olaparib ondansetron osimertinib paclitaxel palbociclib pazopanib pimozide ⁵ quetiapine ⁴ quinidine ⁴ regorafenib rilpivirine ⁵ rivaroxaban ⁵ romidepsin saquinavir ⁵ sildenafil ⁵ simvastatin ⁵ sirolimus ^{4,5} sonidegib sunitinib tacrolimus ^{4,5} tamoxifen tadalafil ⁵ telaprevir temsirolimus teniposide tetracycline				

CYP3A4 substrates	Strong Inhibitors ¹	Moderate Inhibitors	Strong Inducers	Moderate Inducers
ticagrelor ⁵ tipranavir ⁵ tolvaptan ⁵ triazolam ⁵ trimethoprim vardenafil ⁵ vemurafenib venetoclax ⁵ vinca alkaloids zolpidem				

¹ Certain fruits, fruit juices and herbal supplements (star fruit, Seville oranges, pomegranate, gingko, goldenseal) may inhibit CYP 3A4 isozyme, however, the degree of that inhibition is unknown.

²Refer to [Section 4.2.2.1](#) regarding use of corticosteroids.

³The effect of grapefruit juice (strong vs moderate CYP3A4 inhibition) varies widely among brands and is concentration-, dose-, and preparation-dependent.

⁴Narrow therapeutic range substrates

⁵Sensitive substrates (drugs that demonstrate an increase in AUC of ≥ 5 -fold with strong inhibitors)

APPENDIX IV: TOXICITY-SPECIFIC GRADING**Bilirubin**

Grade 1:	> ULN- \leq 1.5 x ULN
Grade 2:	> 1.5 x ULN - 3.0 x ULN
Grade 3:	> 3.0 x ULN -10.0 x ULN
Grade 4:	> 10.0 x ULN

ALT: For the purpose of this study, the ULN for SGPT is 45 U/L regardless of baseline.

Grade 1:	> 45 U/L - \leq 135 U/L
Grade 2:	136 U/L - 225 U/L
Grade 3:	226 U/L - 900 U/L
Grade 4:	> 900 U/L

AST: For the purpose of this study, the ULN for SGOT is 50 U/L regardless of baseline.

Grade 1:	> 50 U/L - \leq 150 U/L
Grade 2:	151 U/L -250 U/L
Grade 3:	251 U/L -1000 U/L
Grade 4:	> 1000 U/L

GGT:

Grade 1:	> ULN- 2.5 x ULN
Grade 2:	> 2.5 x ULN - 5.0 x ULN
Grade 3:	> 5.0 x ULN -20.0 x ULN
Grade 4:	> 20.0 x ULN

APPENDIX V: BAY 1895344 (elimusertib) DOSING NOMOGRAM**Patients < 18 years of Age Part A and B:**

Dose Level 1: BAY 1895344 (elimusertib) Dose Assignment: 24 mg/m²/dose PO BID			
BSA (m²)	Starting Dose Dose to be administered (PO) 3 days on 4 days off per week	Dose Reduction Dose to be administered (PO) 3 days on 4 days off per week	Percent Reduction
0.74-0.94	20 mg BID	20 mg Q AM and 10 mg Q PM	25%
0.95-1.15	30 mg Q AM and 20 mg Q PM	20 mg Q AM and 10 mg Q PM	40%
1.16-1.35	30 mg BID	20 mg BID	35%
1.36-1.56	40 mg Q AM and 30 mg QPM	30 mg Q AM and 20 mg Q PM	30%
≥ 1.57	40 mg BID	30 mg BID	25%

Dose Level -1: BAY 1895344 (elimusertib) Dose Assignment: 18 mg/m²/dose PO BID			
BSA (m²)	Starting Dose Dose to be administered (PO) 3 days on 4 days off per week	Dose Reduction Dose to be administered (PO) 3 days on 4 days off per week	Percent Reduction
0.74-0.94	20 mg Q AM and 10 mg Q PM	10 mg BID	35%
0.95-1.35	20 mg BID	20 mg Q AM and 10 mg Q PM	25%
1.36-1.56	30 mg Q AM and 20 mg Q PM	20 mg Q AM and 10 mg Q PM	40%
≥ 1.57	30 mg BID	20 mg BID	35%

Patients ≥18 years of age on Part B receiving the starting dose of 40 mg BID, the dose reduction for toxicity should be to 30 mg BID, 3 days on 4 days off per week (25% dose reduction).

APPENDIX VI: MEDICATION DIARY FOR BAY 1895344 (elimusertib)

COG Patient ID: _____ Acc# _____

Institution: _____

Please do not write patient names on this form.

Complete each day with the time and dose given for BAY 1895344 (elimusertib). If a dose is not due or is accidentally skipped leave that day blank. **Make note of other drugs and supplements taken under the Comments section below.** BAY 1895344 (elimusertib) tablets should not be crushed but should be swallowed whole. If you vomit after taking a dose, the dose should NOT be repeated. If you miss or forget a dose, it can be taken up to 8 hours before the next dose is due. Otherwise the dose should be skipped. If tablet is broken and the powder of the tablet gets on skin, wash the exposed area with as much water as necessary. Inform your study doctor or nurse if that occurs. BAY 1895344 (elimusertib) should be taken on an empty stomach (1 hour before or 2 hours after a meal) with plenty of water. Add the dates to the calendar below and return the completed diary and the empty bottle or any leftover tablets the study clinic at each visit (weekly during Cycle 1, and then after each treatment cycle).

EXAMPLE			Number of BAY 1895344 (elimusertib) tablets	Comments	
	Date	Time	10 mg	20 mg	
Day 1	1/15/19	8:30 AM	1	1	He felt nauseated an hour after taking the drug but did not vomit.

Cycle #: _____		Start Date: / / / /	End Date: / / / /	Dose Level: _____ mg/m ² /dose	Part of Study:
WEEK 1	Date	Time	# of 10 and/or 20 mg tablets prescribed to take		Comments (Describe any missed or extra doses, vomiting and/or bothersome effects.)
			10 mg	20 mg	
			AM# _____	AM# _____	
			PM# _____	PM# _____	

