3	20	2	1	0	---
4 (MTD)	40	2	2	0	---
5	80	3	2	2	G4 neutropenia; G4 leukopenia & G4 thrombocytopenia
6	60	8	7	2	G4 neutropenia & G3 leukopenia; G2 fatigue
7	60*	4	3	2	G3 thrombocytopenia; G3 neutropenia

* Patients in this cohort were given a 3 day on and 4 day off schedule for 2 weeks followed by 1 week off drug

2.3.3 Pharmacokinetics:

In humans, BAY 1895344 (elimusertib) is 96-97.5% protein bound, primarily binding to albumin. Relative bioavailability comparison of the oral suspension and 40 mg tablets in adults has been completed. At the 40 mg dose level in adults the 40 mg tablet geometric (%CV) T_{max} was 1 (1-1) h, C_{max} 1468 μ g/L (37%), and AUC_{0-24h} 10437 μ g•h/L (61%).

Preliminary PK from the first-in-human study ([Figure 9](#)) show that after oral administration BAY 1895344 (elimusertib) is rapidly absorbed with a median T_{max} of 1 hour and a geometric mean

THIS PROTOCOL IS FOR RESEARCH PURPOSES ONLY, SEE PAGE 1 FOR USAGE POLICY

terminal half-life of 11.5 hours.¹⁶ In the dose expansion portion of the trial, 64 patients had first dose pharmacokinetics and 52 patients had repeat sampling on day 10 at the 40 mg BID dose level on the 3 day on 4 day off schedule. On day 1, the C_{max} was 1226 μ g/L (3 μ M), AUC_{0-12h} was 7118 μ g \cdot h/L (17 μ M \cdot h); on day 10, the C_{max} was 1661 μ g/L (4 μ M) and AUC_{0-12h} was 11539 μ g \cdot h/L (28 μ M \cdot h). Unit conversion was based on BAY 1895344 (elimusertib) MWT 412 g/mol). Exposure was observed to be broadly dose-proportional across the dose range investigated (5-80 mg), and accumulation was consistent with observed half-life.¹⁶

2.3.4 Pharmacodynamics:

Pre-therapy and on-therapy biopsies were obtained during the dose escalation and studied for increased expression of pH2AX and pKAP1. For example, a patient with BRCA1 mutant ovarian cancer who had stable disease demonstrated increased pH2AX and pKAP1; this increase in DNA damage markers was evident in many of the matched tumor pairs, as shown in [Figure 10](#).¹⁶

2.3.5 Efficacy:

In the dose escalation of the first-in-human study of BAY 1895344 (elimusertib), 4 of 20 patients treated in the dose escalation exhibited a partial response (PR) ([Figure 11](#)). Notably, all 4 of these responders had ATM loss of expression on immunohistochemistry and/or ATM loss of function mutations.¹⁶

[figure not shown]
[figure not shown]

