2.5 Overview of Proposed Pediatric Study

2.5.1 Rationale for starting dose and dose finding:

We propose a Phase 1/2 study of BAY 1895344 (elimusertib) monotherapy in pediatric patients with advanced non-central nervous system (CNS) solid tumors or lymphomas that harbor specific genetic alterations in DNA damage repair pathways as well as pre-selected histologies with anticipated susceptibility to ATR inhibition including Ewing Sarcomas (EWS) and PAX3-FOXO1 ARMS.

BAY 1895344 (elimusertib) tablets will be given orally twice daily for 3 days followed by 4 days without drug administration. This trial will use 10 mg and 20 mg tablets. Dosing will be administered according to a BSA based dosing nomogram. The pediatric dose was extrapolated from the adult RP2D and MTD of 40 mg BID 3 days on/4 days off weekly adjusted for BSA. Using

THIS PROTOCOL IS FOR RESEARCH PURPOSES ONLY, SEE PAGE 1 FOR USAGE POLICY

average adult BSA of 1.7 m², the corresponding pediatric dose of BAY 1895344 (elimusertib) is 24 mg/m²/dose BID 3 days on and 4 days off, repeated 4 times per cycle (28-day cycle). Patients who do not have progression of disease or meet other criteria for discontinuation of protocol therapy may continue BAY 1895344 (elimusertib) for up to 26 cycles (since each cycle is 28 days, 26 cycles is equal to 2 years of treatment).

2.5.2 Rationale for Phase 2 Cohorts and Biomarker Selected Cohorts:

The initial Phase 1 portion will utilize the Rolling 6 design and will initially treat pediatric patients at dose level 1 (24 mg/m²/dose), approximately the adult RP2D. If this dose level is not well tolerated, we will next evaluate dose level -1 (18 mg/m²/dose), a 25% dose reduction. The RP2D will be the highest dose level for which < 33% of evaluable patients experience a dose limiting toxicity during Cycle 1. Once the RP2D is defined, a PK expansion cohort will be opened and will enroll up to 6 additional patients for PK analysis. Three phase 2 expansion cohorts will also open for enrollment:

- (1) EWS cohort
- (2) PAX3-FOXO1 ARMS cohort
- (3) DDR cohort

The Phase 2 cohorts will initially open concurrently with the Phase 1 portion but will only enroll patients at least 18 years of age. Patients <18 years of age will be included in the Phase 2 cohorts only after the RP2D/MTD has been estimated in the Phase 1 portion.

Eligibility criteria for the phase 1 and 2 portions of the study will be identical except for the following:

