5.0 TREATMENT PLAN

5.1 Overview of Treatment Plan

Week	Day	Agent
1	1-3	BAY 1895344 (elimusertib) PO BID
	4-7	
2	8-10	BAY 1895344 (elimusertib) PO BID
	11-14	
3	15-17	BAY 1895344 (elimusertib) PO BID
	18-21	
4	22-24	BAY 1895344 (elimusertib) PO BID
	25-28	End of Cycle on day 28

A cycle of therapy is considered to be 28 days. A cycle may be repeated for a total of 26 cycles, up to a total duration of therapy of approximately 24 months.

Drug doses should be adjusted based on the BSA calculated from height and weight measured within 7 days prior to the beginning of each cycle. The starting dose for patients \geq 18 years of age is 40 mg BID 3 days on and 4 days off per week.

If a patient vomits within 30 minutes after the dose of BAY 1895344 (elimusertib) is administered, that dose should NOT be repeated.

On days that BAY 1895344 (elimusertib) is due to be given, it should be administered twice daily, preferably at the same time of day each day. Take BAY 1895344 (elimusertib) on an empty stomach one (1) hour before or two (2) hours after a meal with plenty of water. If a dose of BAY 1895344 (elimusertib) is missed and it is less than 4 hours since the scheduled dosing time, the dose should be taken immediately, otherwise the dose should be skipped.

Patient or caretaker must complete the medication diary with the date, time and number of agent tablets taken each day ([see Appendix VI](#)). The medication diary should be reviewed after completion of each treatment cycle and loaded into Rave.

See [Section 5.6](#) for Therapy Delivery Maps for each cycle.

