5.2 Criteria for Starting Subsequent Cycles

A cycle may be repeated every 28 days if the patient 1) has at least stable disease 2) all pre-cycle studies required per [Section 8.1](#) meet eligibility criteria-as defined in [Section 4.0](#) and 3) is otherwise eligible to continue agent administration per the requirements in [Section 6.0](#).

5.2.1 Recommendations for Starting Each Weekly 3-day Course:

BAY 1895344 (elimusertib) is administered on a 3-day on and 4-day off schedule, repeated 4 times each cycle. Hematologic toxicities are the most common toxicities with BAY 1895344 (elimusertib). Eligibility criteria require an ANC \geq 1000/ μ L and Platelets \geq 100,000/ μ L, hence these parameters also need to be met to start any cycle (See [section 4.1.11.1](#)). Once a cycle has started, patients are required to have an ANC $>$ 500/ μ L and Platelets $>$ 50,000/ μ L within 48 hours prior to initiation of each 3 day interval of BAY 1895344 (elimusertib) administration (i.e. ANC and platelet parameters must be met (without transfusion) within 48 hours of initiation of days 8, 15, and 21). If parameters are not met, this 3-day interval of BAY 1895344 (elimusertib) will be omitted and attempted to restart the following week (e.g. day 15 or 21). If more than one 3-day block of BAY 1895344 (elimusertib) is missed within a cycle (i.e. $<$ 75% of planned therapy is given for a particular cycle), that would be considered a hematologic DLT.

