- ⁶ Must be obtained within 72 hours of the start of each cycle and on day 15 of all subsequent cycles. If patients develop Grade 4 neutropenia or Grade 3 or 4 thrombocytopenia, CBC/differential/platelets should be checked at least twice weekly (every 3-4 days) until recovery to Grade 3 neutropenia, Grade 2 thrombocytopenia or until the criteria for dose limiting toxicity are met. For patients who experience hematological dose limiting toxicity, CBCs should be checked at least weekly until recovery of ANC and platelet count to eligibility criteria. Patients who have a dose adjustment due to hematologic toxicity attributable to BAY 1895344 (elimusertib), are required to have CBCs checked once weekly to confirm the safety of this adjusted dose during the cycle. Please see [Section 6.1](#) for details.
- ⁷ If greater than 7 days from pre study labs, please collect CBC, differential, platelets, bilirubin, albumin and serum creatinine within 48 hours prior to cycle 1, dose 1. These labs must still meet eligibility to receive dose 1 (as per [Section 4.0](#)).

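### The diary's missed-dose rule conflicts with Section 5.1 for the last dose of each 3-day block, because it does not exclude the rest days (minor wording fix)

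*Combined protocol and SAP*

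**What the plan says.** Two current passages tell people what to do about a late dose.

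- **Section 5.1 (treatment plan)** counts from the scheduled time. If it is "less than 4 hours since the scheduled dosing time, the dose should be taken immediately, otherwise the dose should be skipped".
- **Appendix VI (medication diary)** counts back from the next dose: "If you miss or forget a dose, it can be taken up to 8 hours before the next dose is due". After that point the diary also says to skip.

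The schedule is twice daily on Days 1–3, 8–10, 15–17 and 22–24 of a 28-day cycle (Section 5.1 and the Therapy Delivery Maps in 5.6 and 5.7). Section 2.5.1 describes it as "given orally twice daily for 3 days followed by 4 days without drug administration".

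The diary's only reference to days without a dose is about filling in the form: "If a dose is not due or is accidentally skipped leave that day blank".

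**The concern.** A rule tied to the next dose works only while the next dose is a fixed, short time away. In this schedule it is not: after the evening dose on Days 3, 10, 17 and 24 the next dose falls on the first morning of the following block. A family that remembers the Day 3 evening dose on the morning of Day 4 would find the diary allowing it and Section 5.1 forbidding it. By following the study's own form, they would depart from the treatment plan.

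The drug is myelosuppressive, and each block starts only if neutrophil and platelet counts are adequate. Section 5.2.1 requires those counts "within 48 hours of initiation of days 8, 15, and 21" (the dosing schedule puts the last of these blocks at Day 22). The at-home instruction should therefore match the plan. A very late dose on Days 6–7 could also come after the count meant to clear the next block.

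**Working it through.** **Inputs**

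- Section 5.1 window: less than 4 hours after the scheduled time.
- Diary window: until 8 hours before the next dose.
- Doses per cycle: 2 × 12 dosing days = 24.
- Clock times: 08:00 and 20:00. This is an assumption, because Section 5.1 fixes no interval. Section 8.3.5.2 supports about 12 hours, since it treats the 12-hour sample as the trough before the next dose. A range of 10 to 14 hours is also shown.
- Half-life, adults only: Section 2.3.3 gives a geometric mean "terminal half-life of 11.5 hours"; the Figure 9 table gives 9.81 hours for the 40 mg BID dose expansion.

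**Step 1. Inside a block.** Diary window = hours to next dose − 8 = 12 − 8 = 4 hours. This reproduces the Section 5.1 figure, so 20 of 24 doses show no conflict at 12-hour spacing. (At exactly 4 hours the wordings differ, which is trivial.)

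**Step 2. Last dose of a block.** Day 3 20:00 to Day 8 08:00 is 5 × 24 − 12 = 108 hours. The diary window is 108 − 8 = 100 hours, ending at 00:00 on Day 8, against less than 4 hours in Section 5.1. Four doses per cycle are affected: 4/24 = 17%.

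**Step 3. Other spacings (morning dose at 08:00).**

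| Evening dose | Diary window inside a block | Diary window at block end |
|---|---|---|
| 18:00 (10 h) | 2 or 6 h | 110 − 8 = 102 h |
| 20:00 (12 h) | 4 h | 108 − 8 = 100 h |
| 22:00 (14 h) | 6 or 2 h | 106 − 8 = 98 h |

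**Step 4. Effect on exposure.** Fraction of the late dose left at the next block = 2^(−t / half-life), assuming a single decline rate.

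- Likely case, taken Day 4 08:00: t = 96 hours. 2^(−96/9.81) = 0.11%; 2^(−96/11.5) = 0.31%. A 96-hour rest remains.
- Last permitted time, Day 8 00:00: t = 8 hours. 2^(−8/9.81) = 57%; 2^(−8/11.5) = 62%. The patient has by then been off drug since Day 3 08:00, which is 4 × 24 + 16 = 112 hours. The two blocks become 5 + 7 doses instead of 6 + 6.

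**Step 5. Overlap with the safety counts.** For Days 3, 10 and 17, the count window is 48 hours before the block and the diary permission ends 8 hours before it: 48 − 8 = 40 hours of overlap. After Day 24, Section 8.1 footnote 6 applies to the pre-cycle count: "Must be obtained within 72 hours of the start of each cycle". That gives 72 − 8 = 64 hours.

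**Step 6. Decision rules.** The missed-dose DLT criterion in Section 5.5.2 counts only delays due to myelosuppression, so a forgotten dose does not trigger it. If all four block-end doses in a cycle were skipped, 20/24 = 83% of doses would remain, above the 75% needed for DLT evaluability in Section 11.2.1.

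**The case against.** The strongest reply is that no sensible family would read the diary this way. Its wording is a natural lay version of the 4-hour rule for twice-daily dosing, and it gives the right answer for 20 of 24 doses. The grid has rows only for dosing days. Families are told to leave a day blank when no dose is due, to note missed or extra doses, and to return the diary and leftover tablets weekly in Cycle 1. A rest-day dose in the DLT window would therefore come to light within about a week. Youth information sheets and consent pages are not in the text available here and may explain the rest days.

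This stands as an argument about likelihood and size. It does not remove the permission: those are instructions for recording and returning, and none says when a missed dose stops being allowed. The point concerns the diary, not everything patients are told.

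Two technical objections also have some force.

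- The half-life figures look more precise than they are. The 9.81-hour value carries a 54% coefficient of variation, and adult cohort values in the Figure 9 table run from 8.61 to 17.8 hours. Over that range the likely case becomes 2^(−96/8.61) = 0.04% to 2^(−96/17.8) = 2.4%, still small. The midnight case becomes 2^(−8/8.61) = 53% to 2^(−8/17.8) = 73%, but it is not realistic.
- The count overlap for Days 3 and 17 in Cycles 2+ depends on the Section 5.2.1 counts, because Section 8.1 footnote 6 routinely schedules only a pre-cycle and a Day 15 count. Nothing in the documents shows that one shifted dose would invalidate a count.

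**Conclusion.** The point holds, at minor severity. For the evening dose of Days 3, 10, 17 and 24, the diary as written allows about 100 hours (98 to 102 over plausible spacings) where Section 5.1 allows less than 4, and it does not exclude the drug-free days. The conflict needs only twice-daily dosing and the 4-day rest; it does not depend on exact clock times.

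The expected consequence is small. The dose is moved, not added, and the rest is shifted, not lost. In the likely case almost none of the late dose remains at the next block. The size of that effect rests on adult pharmacokinetics. No DLT criterion, Simon rule, sample size or analysis changes. The case for acting is that a patient-held instruction for a myelosuppressive drug should not permit what the treatment plan forbids.

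**What to change.** Replace the diary sentence with the Section 5.1 rule in plain words, for example: *If you miss a dose, take it only if fewer than 4 hours have passed since it was due. Otherwise skip it, and do not make it up later on a rest day.*

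Counting from the scheduled time also removes the 2-to-6-hour drift inside a block when doses are not 12 hours apart. At 12-hour spacing the other 20 doses are unaffected. The cost is one changed sentence, a form revision and reissue to sites.
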